#### **4.2.1.2 Hematologic DLT:**

After the 42 day period and confirmed hematologic DLT: If peripheral blasts are absent AND bone marrow blasts are less than 5%, then the patient may restart study treatment on cycle 2 at the next lower dose level.

After achieving CR, the dose level may be re-escalated at the initiation of next cycle at the discretion of the investigator.

### **4.2.2 Dose Delays/Dose Modifications for Non-DLTs**

#### **4.2.2.1 Induction**

Patients experiencing non-DLT toxicities during induction related believed to be due to TP-0903 therapy that present a challenge to medical management (i.e. grade 2 chronic nausea, myalgia, or fatigue) should have their dose held until it falls to a level of grade 1 or < and then re-start at a -1 dose reduction in therapy. If this recurs at the lower dose, the patient will discontinue TP-0903 and be followed on the treatment regimen.

#### **4.2.2.2 Maintenance**

##### **Non-hematologic toxicities**

Dose modifications due to TP-0903: Patients experiencing grade 3 non-hematologic toxicities believed to be related to TP-0903 therapy (excluding correctable electrolyte abnormalities), select grade 2 toxicities (neurologic), or chronic grade 2 toxicity that presents a challenge to medical management (i.e. grade 2 chronic nausea, myalgia, or fatigue) should have their TP-0903 dose held until this resolves to grade 1 or < and then it may be initiated at a dose level below the treating dose. If this recurs at the lower dose, the patient will discontinue TP-0903 and be followed on the treatment regimen. Patients experiencing any grade 4 non-hematologic toxicities will have treatment discontinued permanently.

##### **Hematologic toxicities**

TP0903 dose reductions in subsequent cycles after CR/CRI is achieved (i.e., Subsequent cycles after being in CR/CRI for at least 1 cycle) will depend on the counts prior to starting the preceding cycle.

- a) If prior to the previous cycle (for e.g., patient is starting C5, check the counts prior to starting C4) if the counts were: WBC  $\geq$  3.0  $\times 10^9$ /L, ANC  $\geq$  1.5  $\times 10^9$ /L, and platelets  $\geq$  75.0  $\times 10^9$ /L (all three must apply), adjust the dose as follows, based on nadir counts of the prior cycle (per the e.g. above the prior cycle will be C4):

Nadir Counts		% Dose TP- 0903 in the Next Course
ANC ( $\times 10^9/L$ )*	Platelets ( $\times 10^9/L$ )*	
<0.5	<25.0	50%

\* Dose reductions applies when either ANC OR Platelets are at these values

#### 4.3 General Administration Guidelines

##### 4.3.1 Missed or Vomited Doses

Missed or vomited doses will not be made up. The patient will follow regular schedule starting the next study dosing day. All missed doses should be documented in the patient diary. If a dose is vomited within one hour of ingestion, it will be considered a missed dose and recorded as such on the patient diary. If vomiting occurs more than 1 hour after dosing, it will still be considered a complete dose.

### 5. Safety and Reporting Requirements

#### 5.1. Assessment of Safety

Safety assessments will consist of monitoring and recording adverse events (and serious adverse events); measurements of protocol-specified hematology, clinical chemistry, and other laboratory variables; measurement of protocol-specified vital signs; and other protocol-specified tests that are deemed critical to the safety evaluation of the study drug and should be consistent with institutional standards and Good Clinical Practice.

#### 5.2. Definitions

##### 5.2.1. Adverse Events (AE)

An AE is any unfavorable and unintended sign, symptom, or disease temporally associated with the use of an investigational (medicinal) product or other protocol-imposed intervention, regardless of attribution. For the purposes of this clinical study, adverse events include only treatment-emergent events which are either new or represent detectable exacerbations of pre-existing conditions.

##### This includes the following:

- Subjective or objective symptoms spontaneously offered by the subject and/or observed by the investigator or study staff including laboratory abnormalities of clinical significance.
- Any adverse events experienced by the subject through the completion of final study procedures.
- AEs not previously observed in the subject that emerge during the protocol-specified AE reporting period, including signs or symptoms associated with MCL that were not present before the AE reporting

period

- Complications that occur as a result of protocol-mandated interventions (eg, invasive procedures such as biopsies)

**The following are NOT considered an adverse event:**

- **Pre-existing condition:** A pre-existing condition (documented on the medical history CRF) is not considered an AE unless the severity, frequency, or character of the event worsens during the study period.
- **Preplanned hospitalization:** A hospitalization planned before signing the informed consent form is not considered an SAE, but rather a therapeutic intervention. However, if during the pre-planned hospitalization an event occurs, which prolongs the hospitalization or meets any other SAE criteria, the event will be considered an SAE. Surgeries or interventions that were under consideration but not performed before enrollment in the study will not be considered serious if they are performed after enrollment in the study for a condition that has not changed from its baseline level. Hospitalizations for social reasons or due to long travel distances are also not SAEs.
- **Diagnostic Testing and Procedures:** Testing and procedures should not be reported as adverse events or serious adverse events, but rather the cause for the test or procedure should be reported.

### **5.2.2. Serious Adverse Event**

The terms “severe” and “serious” are not synonymous. Severity (or intensity) refers to the grade of an AE (see below). “Serious” is a regulatory definition and is based on patient or event outcome or action criteria usually associated with events that pose a threat to a patient’s life or functioning. Seriousness (not severity) serves as the guide for defining regulatory reporting obligations to applicable regulatory authorities.

A serious adverse event (experience) or reaction is any untoward medical occurrence that at any dose:

- It results in death (i.e., the AE actually causes or leads to death).
- It is life-threatening (with regards to determining if an AE is serious, “life-threatening” is defined as an AE in which the subject was at risk of death at the time of the event. It does not refer to an event which hypothetically might have caused death if it were more severe. If either the investigator or the Sponsor believes that an AE meets the definition of life-threatening, it will be considered life-threatening.).
- It requires or prolongs in-patient hospitalization.
- It results in persistent or significant disability/incapacity (i.e., the AE results in substantial disruption of the patient’s ability to conduct normal life functions).
- It results in a congenital anomaly/birth defect in a neonate/infant born to a mother exposed to the investigational product.
- It is considered a significant medical event by the investigator based on medical judgment (e.g., may jeopardize the patient or may require medical/surgical intervention to prevent 1 of the outcomes listed

above).

### **5.2.3. Severity**

Definitions found in the Common Terminology Criteria for Adverse Events version 5.0 (CTCAE v5.0) will be used for grading the severity (intensity) of AEs. The CTCAE v5.0 displays Grades 1 through 5 with unique clinical descriptions of severity for each referenced AE. Should a patient experience any AE not listed in the CTCAE v5.0, the following grading system should be used to assess severity:

- Grade 1 (Mild AE) – experiences which are usually transient, requiring no special treatment, and not interfering with the patient's daily activities
- Grade 2 (Moderate AE) – experiences which introduce some level of inconvenience or concern to the patient, and which may interfere with daily activities, but are usually ameliorated by simple therapeutic measures
- Grade 3 (Severe AE) – experiences which are unacceptable or intolerable, significantly interrupt the patient's usual daily activity, and require systemic drug therapy or other treatment
- Grade 4 (Life-threatening or disabling AE) – experiences which cause the patient to be in imminent danger of death
- Grade 5 (Death related to AE) – experiences which result in patient death

### **5.2.4. Suspected Adverse Reaction**

- A Suspected Adverse Reaction is any adverse event for which there is a “reasonable possibility” that the drug caused the adverse event.
- “Reasonable Possibility”, for the purposes of safety reporting, means there is evidence to suggest a causal relationship between the drug and the adverse event. Examples of evidence that would suggest a causal relationship between the drug and the adverse event are:
  - A single occurrence of an event that is uncommon and known to be strongly associated with drug exposure (e.g., angioedema, blood dyscrasias, rhabdomyolysis, hepatic injury, anaphylaxis, and Stevens-Johnson Syndrome).
  - One or more occurrences of an event that is not commonly associated with drug exposure, but is otherwise uncommon in the population exposed to the drug (e.g., include tendon rupture or heart valve lesions in young adults, or intussusception in healthy infants). If the event occurs in association with other factors strongly suggesting causation (e.g., strong temporal association, event recurs on rechallenge), a single case may be sufficiently persuasive; but often, more than one occurrence (from one or multiple studies) would be needed before the sponsor could make a determination of whether the drug caused the event.
  - An aggregate analysis of specific events that can be anticipated to occur in the study population independent of drug exposure. Such events include known consequences of the underlying disease or condition under investigation (e.g., symptoms or disease progression), or events unlikely to be related to the underlying disease or condition under investigation, but commonly occur in the study population

independent of drug therapy (e.g., cardiovascular events in an elderly population). An aggregate analysis (across studies) will identify those events that occur more frequently in the drug treatment group than in a concurrent or historical control group.

### **5.2.5. Unexpected**

An “unexpected” AE is an AE that is not listed in the Investigator Brochure or is not listed at the specificity or severity that has been observed. For example, hepatic necrosis would be “unexpected” (by virtue of greater severity) if the Investigator Brochure referred only to elevated hepatic enzymes or hepatitis. “Unexpected” also refers to AEs that are mentioned in the Investigator Brochure as occurring with a class of drugs or as anticipated from the pharmacological properties of the drug, but are not specifically mentioned as occurring with the study drug under investigation.

## **5.3. Documenting and Reporting of Adverse Events (AEs) and Serious Adverse Events (SAEs)**

The Sponsor-investigator is responsible for ensuring that all AEs and SAEs that are observed or reported during the study, as outlined in the prior sections, are recorded on the case report form (CRF). All SAEs also must be reported according to the OSU IRB guidelines.

### **5.3.1. Adverse Event Reporting Period**

The AE reporting period for this study begins after first dose of study drug administration until 30 days after discontinuation of the study drug. All AEs and SAEs that are encountered during the protocol specified AE reporting period should be followed to resolution or until the investigator assesses the patient as stable, a new anti-cancer therapy is initiated, or the patient is lost to follow up or withdrawals consent Resolution/stable means the subject has returned to baseline state of health or the Investigator does not expect any further improvement or worsening of the event.

### **5.3.2. Assessment of Adverse Events**

Investigators will assess the occurrence of AEs and SAEs at all patient evaluation time points during the study. All AEs and SAEs whether volunteered by the patient, discovered by study personnel during questioning, or detected through physical examination, clinically significant laboratory test, or other means will be recorded in the patient’s medical record and on the AE CRF and, when applicable, on an SAE/Event reporting form.

Each recorded AE or SAE will be described by its duration (i.e., start and end dates), severity, regulatory seriousness criteria, if applicable, suspected relationship to the investigational product (see following guidance), and any actions taken.

All deaths should be reported with the primary cause of death as the AE term, as death is typically the outcome of the event, not the event itself. The primary cause of death on the autopsy report should be the term reported.

An SAE will qualify for expedited reporting to regulatory authorities if the SAE is considered a Suspected Adverse Reaction and is not listed in the current Investigator’s Brochure (i.e., an unexpected event). To ensure consistency of AE and SAE causality assessments, investigators should apply the following general guideline:

Fatal	Adverse event resulted in death.
--------------	----------------------------------

Unrelated	Another cause of the adverse event is more plausible; a temporal sequence cannot be established with the onset of the adverse event and administration of the investigational product; or, a causal relationship is considered biologically implausible.
Possibly Related	There is a clinically plausible time sequence between onset of the adverse event and administration of the investigational product, but the adverse event could also be attributed to concurrent or underlying disease, or the use of other drugs or procedures. Possibly related should be used when the investigational product is one of several biologically plausible adverse event causes.
Definitely Related	The adverse event is clearly related to use of the investigational product.

#### **5.4. Procedures for Reporting Drug Exposure During Pregnancy and Birth Events**

Before study enrollment, subjects must agree to take appropriate measures to avoid pregnancy (See Section 4.2.4). Report any pregnancy that occurs in a patient or patient's partner from the time of consent to 30 days after the last dose of study drug. Record any occurrence of pregnancy in the patient's medical records and notify the treating physician within 24 hours of learning of the event. Abortion, whether therapeutic, elective or spontaneous, will be reported as an SAE.

A patient must immediately inform the investigator if the patient or patient's partner becomes pregnant from the time of consent to 30 days after the last dose of study drug. Any female patients receiving TP-0903 PO who become pregnant must immediately discontinue the drug. The investigator should counsel the patient, discussing any risks of continuing the pregnancy and any possible effects on the fetus. Although pregnancy itself is not regarded as an AE, the outcome will need to be documented. Report any pregnancy that occurs in a subject or subject's partner from the time of consent to 30 days after the last dose of study drug. Record any occurrence of pregnancy on appropriate case report form and send it to Sumitomo Dainippon Pharma Oncology, Inc. (SDPO), or designee, within 24 hours of learning of the event. The pregnant female will be followed for outcome, which is defined as elective termination of the pregnancy, miscarriage, or delivery of the fetus. For pregnancies with an outcome of live birth, the newborn infant will be followed until 30 days old by completing the Pregnancy Report Form Part II. Any congenital anomaly/birth defect noted in the infant must be reported as an SAE.

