## 2. Patient Selection

### 2.1. Eligibility Criteria

**2.1.1.** Patients age  $\geq 18$  with relapsed/refractory AML and the presence of *FLT3*-ITD mutation.

**2.1.2.** Patients with secondary AML or therapy related disease (t-AML) are eligible.

**2.1.3.** If the patient has co-morbid medical illness, life expectancy attributed to this must be greater than 6 months.

**2.1.4.** ECOG performance status  $\leq 2$

**2.1.5.** Patients must have adequate organ function as defined below:

- Total bilirubin  $< 2.0 \text{ mg/dL}$  unless due to Gilbert's disease
- AST (SGOT)/ALT (SGPT)  $< 2.5 \times$  institutional upper limit of normal
- Cr clearance  $> 50 \text{ mL/min}$  by Cockcroft-Gault calculation
- NYHA CHF Class II or better
- Cardiac ejection fraction  $\geq 40\%$

**2.1.6.** Female patients of child-bearing potential must agree to use dual methods of contraception and have a negative serum pregnancy test at screening, and male patients must use an effective barrier method of contraception if sexually active with a female of child-bearing potential. Acceptable methods of contraception are condoms with contraceptive foam, oral, implantable or injectable contraceptives, contraceptive patch, intrauterine device, diaphragm with spermicidal gel, or a sexual partner who is surgically sterilized or post-menopausal. For both male and female patients, effective methods of contraception must be used throughout the study and for three months following the last dose.

**2.1.7.** Ability to understand and willingness to sign the written informed consent document.

**2.1.8.** HIV infection without history of AIDS and sufficiently high CD4 cells ( $> 400/\text{mm}^3$ ) and low

HIV viral loads (<30,000 copies/ml plasma) not requiring anti-HIV therapy are eligible.

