### **3.1. Duration of Follow-up**

Patients will be followed monthly for treatment failure until the time of transplant or maintenance therapy, at which time they will go to clinical follow-up, followed every 3 months for up to 2 years from registration and then every 6 months for up to 5 years from registration until relapse or death. Patients who end treatment for reasons other than relapse or a subsequent AML treatment (excluding transplant) will follow the same clinical follow-up schedule. Patients who relapse or receive a subsequent AML therapy (excluding transplant) will go to survival follow-up, followed every 6 months for 5 years from registration until death or the completion of the study. A survival follow-up visit can be conducted by phone or electronic contact with the patient or authorized representative. Please see the study calendar in Section 9 for details.

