 Bone marrow (BM) core biopsy and aspiration which will include cytogenetics, flow cytometry, targeted mutational analyses and morphologic assessment. Aspirate (10ml) only is required on day 5 of cycle 1 for correlative studies. Cycle 1, day 28 BM examination will require 10 ml aspirate to be collected for correlative studies. All the specimens for correlative studies will be processed at the OSU Leukemia Tissue Bank. Aspiration only may be acceptable for patients with BM biopsy that falls out of the window, provided AML diagnosis is unequivocal.

 Logistical issues that preclude patient visit on days noted will be allowed under special circumstances but must be discussed with the PI. Should such occasions arise, evaluations should be done as soon as feasible, preferably within 24-48hours

 Correlatives studies to be performed per section 8.2 (+/- 1 day). All patients will have serial peripheral blood sampling where cells are isolated at screening, day 5, day 12, at count recovery, at day 28 of each subsequent cycle (when available) and at time of relapse (in responding patients). Samples will be collected in green top (heparin tubes).

 End of Treatment visit, if applicable, is to be performed 30+7 days following patient last drug administration.

 Patients will be followed monthly for treatment failure until the time of transplant or maintenance therapy, at which time they will go to clinical follow-up, followed every 3 months for up to 2 years from registration and then every 6 months for up to 5 years from registration until relapse or death. Patients who end treatment for reasons other than relapse or a subsequent AML treatment (excluding transplant) will follow the same clinical follow-up schedule. Patients who relapse or receive a subsequent AML therapy (excluding transplant) will go to survival follow-up, followed every 6 months for 5 years from registration until death or the completion of the study. A survival follow-up visit can be conducted by phone or electronic contact with the patient or authorized representative.

TP-0903 monotherapy (Cycles 2-4 and maintenance)

	Cycles 2-4 and maintenance															End of Treatment 	Follow-up 		
	D1	D2	D3	D4	D5	D6	D7	D8	D9	D10	D11	D12	D13	D14	D15	D16	D18	D21	D28
Weight and BSA	x																x	x	x
Physical examination	x						x											x	
Vitals signs	x					x						x					x	x	x

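### Contraception is required for three months after the last dose, but the duty to report a pregnancy stops at 30 days, leaving 59 to 62 days uncovered

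*Combined protocol and SAP*

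**What the plan says.** Section 2.1.6 (Eligibility Criteria) states, for both sexes, that "effective methods of contraception must be used throughout the study and for three months following the last dose".

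Section 5.4 (Procedures for Reporting Drug Exposure During Pregnancy and Birth Events) uses a shorter window, and uses it three times. Two sentences tell the site to report a pregnancy in a patient or a patient's partner "from the time of consent to 30 days after the last dose of study drug". A third obliges the patient to inform the investigator if the patient or partner "becomes pregnant from the time of consent to 30 days after the last dose of study drug". The section then requires a known pregnancy to be followed to termination, miscarriage or delivery, and a live-born infant to be followed until 30 days old. It gives no separate, longer window for that follow-up.

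For the contraception measures themselves, Section 5.4 says that "subjects must agree to take appropriate measures to avoid pregnancy (See Section 4.2.4"). Section 4.2 deals with dose delays and modifications and contains only 4.2.1 and 4.2.2.

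Three other provisions bear on the point:

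- Section 5.3.1 runs adverse event reporting "until 30 days after discontinuation of the study drug".
- Section 5.4 adds: "Although pregnancy itself is not regarded as an AE, the outcome will need to be documented".
- The study calendar in Section 9 places the last treatment-phase contact, the End of Treatment visit, where it "is to be performed 30+7 days following patient last drug administration".

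**The concern.** The protocol treats the three months after the last dose as a period in which pregnancy should be avoided, but for most of that period it asks nobody to report one. The pregnancies left out are those that occur despite the protocol's own precaution, or in breach of it. A site that follows Section 5.4 to the letter has no duty to record such a pregnancy or find out how it ended, and the patient has no duty to mention it.

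What is at stake is the completeness of pregnancy-outcome data for an early-phase agent, where even one lost outcome is lost information. Fetal harm is not shown: the documents do not say whether exposure to TP-0903 persists into the second or third month after dosing. Sample size, error rates, the tolerability check, the toxicity monitoring rule and the efficacy decision are untouched.

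**Working it through.** The plan gives no figure of its own to reproduce. The check is calendar arithmetic, followed by a search for any other rule that would capture a late pregnancy.

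**Inputs**

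- Contraception after the last dose: three months (Section 2.1.6).
- Site reporting and the patient's duty to inform: 30 days after the last dose (Section 5.4).
- End of Treatment visit: 30 to 37 days after the last dose (Section 9, footnote on the visit).

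**Length of the gap**

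Adding three calendar months to every start date from 2019 to 2024 gives between 89 and 92 days.

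Gap = contraception period − reporting period; share = gap ÷ contraception period.

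| Three months taken as | Gap (days) | Share uncovered |
|---|---|---|
| 89 days (shortest calendar case) | 89 − 30 = 59 | 59/89 = 66.3% |
| 90 days | 90 − 30 = 60 | 60/90 = 66.7% |
| 92 days (longest calendar case) | 92 − 30 = 62 | 62/92 = 67.4% |

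Even on a 12-week reading (84 days) the gap is 84 − 30 = 54 days, or 54/84 = 64.3%. If the reporting window matched Section 2.1.6, the gap would be zero.

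**Time left after the last treatment-phase visit**

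Shortest: 89 − 37 = 52 days. Longest: 92 − 30 = 62 days.

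**Does another rule close the gap?**

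- *Adverse event reporting.* It stops at 30 days as well (Section 5.3.1), and Section 5.4 says that a pregnancy is not in itself an adverse event.
- *Outcome and newborn follow-up.* In Section 5.4 these follow the 30-day reporting rule and presuppose that the pregnancy is known.
- *Scheduled contact.* Under Section 3.1, a patient who relapses or starts another AML therapy other than transplant "will go to survival follow-up, followed every 6 months for 5 years from registration". That contact may be by phone or electronic means, and with six months between contacts there may be none in the 52 to 62 days that remain. The patient's duty to inform is then the main safeguard, and it is the duty that lapses at day 30.
- *Cross-reference.* A reader of Section 5.4 who looks for the contraception rule is sent to a section that does not exist. Within 5.4 the only post-treatment window for reporting is 30 days.

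No section extends pregnancy reporting to three months.

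**The case against.** The strongest reply is that two different windows do not contradict each other. Contraception is a precaution asked of the patient; reporting is a data-collection duty that ends with the adverse event period. A site can comply with both, and a sponsor may deliberately set the first longer than the second. This is fair as far as it goes: the point concerns a design choice. But the protocol gives no reason for the difference, and following the stated rule exactly loses information inside the protocol's own precaution period.

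A second reply is that bad outcomes may be captured elsewhere. Section 5.2.1 counts adverse events through the final study procedures. Section 5.4 makes any abortion, and any congenital anomaly, a serious adverse event without repeating the time limit. Section 5.2.2 lists congenital anomaly without a limit. Section 5.5 requires notification of serious, unexpected, suspected reactions seen while the study is running. Section 5.4 also asks that any occurrence of pregnancy be recorded. Some adverse outcomes are therefore arguably reportable after day 30. These routes work only if the pregnancy happens to become known, however, and they sit against the 30-day limit in Section 5.3.1. None creates a clear duty to report a late pregnancy as such.

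Three smaller points stand. The 66 to 67% is a share of days, not of risk or of expected pregnancies. The wrong cross-reference is a clerical error in its own right, and the three-month rule is still seen by anyone who checks eligibility. The consent pages and the pregnancy report form are not available here, so nothing can be said about what patients are told in them.

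**Conclusion.** The concern holds. Sections 2.1.6 and 5.4 set different post-treatment windows, and pregnancies beginning in the last 59 to 62 of the 89 to 92 days need not be reported or followed. Voluntary reporting remains possible, and some adverse outcomes may be picked up under other provisions if they come to light.

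The practical effect is probably small. The plan is to accrue 40 to 46 patients with relapsed or refractory AML, and few pregnancies are expected among them or their partners. That expectation is an assumption, because the documents do not give the number of patients of childbearing potential. This is a low-severity point: a cheap improvement to safety-data completeness with no bearing on any endpoint or decision rule. The reading of the text and the arithmetic are not in doubt.

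**What to change.** At the next amendment:

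1. In the three sentences of Section 5.4 that set the window (two on site reporting, one on the patient's duty to inform), replace 30 days after the last dose with three months after the last dose.
2. Correct the cross-reference in Section 5.4 from 4.2.4 to 2.1.6.
3. At the End of Treatment visit, remind patients that they should tell the site about a pregnancy in themselves or a partner until month three.

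The cost is a few words and a reminder at an existing visit, with no added visit, test or sample. The drawback is that the longer duty depends on patients coming forward: 52 to 62 days remain after the End of Treatment visit, and those in six-monthly survival follow-up may have no scheduled contact in that time. Capture will improve but will not be complete.
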